There are a number of advantages in the use of VRE and these include; repeatability, portability, selfdirected learning, data collection, and cost (8). Taekman et al attribute further human elements such as, instant feedback, rewards, competition, scalability, standardisation and convenience (9).

Virtual Reality Education provides an opportunity to deliberately practise rare, potentially lifesaving procedures and scenarios in a risk-free environment. These advantages make VRE an attractive educational tool, provided that the virtual reality education program is at least as effective or superior to the traditional education method. This remains the motivation behind this pilot study.

3 **Project Aims / Objectives / Hypotheses**

Primary objectives: Compare the effectiveness of VRE training with traditional education methods for the placement of a chest drain by anaesthesia registrars. Effectiveness of education will be assessed by proficiency of chest drain insertion, non-deviation from standardised chest drain checklist and the time taken to complete the task of chest drain insertion.

Secondary Objectives: Assessment of registrar levels of confidence regarding chest drain insertion pre- and post-educational sessions.

Hypothesis: VRE training is as effective if not superior to a traditional teaching approach for the insertion of chest drains.

Null Hypothesis: There is no difference in chest drain insertions outcomes when instructed by either a traditional or VR training approach.

4 Project Design

Project Design

Pilot study

Pre-test survey assessing prior chest drain insertion training; number of chest drain insertions performed in patients; current confidence level related to chest drain insertion ability.

Subjects randomly assigned to one of two groups

Traditional teaching method. Text and instructional video Virtual reality training method

All study participants will be assessed by two anaesthetic consultants blinded to group allocation using a validated checklist for chest drain competency. Chest drain insertion success with be assessed using scores from assessment tool, number of deviations from the checklist, time to task completion and self-reported chest drain insertion confidence levels.

Source and Selection of Participants

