Once all participants have completed their allocated training program and have been subsequently assessed by a blinded assessor the data collection process will end.

5 Treatment of Participants

Description and justification for treatments, interventions or methods to be utilised

The hypothesis that the VRE may prove to be a more effective training method is of potential benefit to all the study participants and patients, especially as this technology becomes more widely incorporated into medical training. The *"Traditionally trained"* group will not be disadvantaged as this is currently the accepted standard of training. Furthermore, access to the VR training software will be made freely available to all participants once their blinded assessment has been completed.

Permitted medications/treatments

There is no medication or treatment in this study.

Monitoring of participant compliance

Onsite facilitators will be present to conduct the virtual reality training session. Facilitators will further ensure that the traditional group reads the notes provided and watches the instructional video.

6 Assessment of Efficacy

Outcomes

Raw scores on the validated chest drain insertion competency checklist

Any deviation from the validated checklist

Time taken for task completion

Matched confidence scores using Likert data from a pre- and post-intervention survey.

Efficacy assessment

The TACTIC validated checklist for chest drain insertion competency will be used (10). The assessors will determine the number of deviations from the checklist and record the time taken to complete the procedure. Confidence levels will be assessed via matched Likert data.

7 Assessment of Safety

Risks and Benefits

Potential risks to the participants include motion sickness, nausea and headaches from the virtual reality training programme. Facilitators will attempt to improve comfort and ensure correct use of the virtual reality headsets in order to limit these effects. Infection risk and cross contamination will be managed by the use of a UVC irradiation device.

Emergent chest drain insertion is a potentially life-saving procedure and the benefits for potentially improving knowledge and skill of chest drain insertion is enormous.

Safety

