Facilitators will be present and monitor for any ill effects developing as a result of the training intervention. Infection control will be provided via UVC irradiation device, used on the virtual reality headset. The controllers will be wiped down with disinfectant wipes between uses.

Adverse events reporting

Any adverse events will be reported via the research team.

- Minor event: follow up with candidate
- More serious event: Regular follow up until resolved/ referral to care provider as determined by independent assessment.

Follow-up of Adverse Events

Any adverse events will be followed up until resolution of any symptoms.

8 Data Management, Statistical Analysis and Record Keeping

Statistics and Interim Analysis

Wilcoxon signed-rank test will be employed to assess any differences that may exist between the two groups. Likert-type questions will be used to obtain self-reported confidence data pre- and post-educational sessions. The median results of the Likert-type questions will be shown to describe central tendency.

Sample Size

The pilot project will use a convenience sample of Anaesthesia registrars at FSFHG. Currently there are 51 registrars. All registrars will be approached to participate. The study is a proof of concept study. Due to the fact that virtual reality software has only recently been developed, there is to the best of our knowledge no other published data to refer to. If a difference is noted between the study groups, a power analysis will be conducted to calculate the sample size necessary in a follow up study, to confirm differences that may exist.

Study Power and Significance

A validated checklist will be used to assess each candidate's placement of a chest drain. This checklist has 20 steps, graded out of 40 points, that must be completed in order for the chest drain placement to be deemed safe & successful. The mean score of the two study groups will be compared. A difference in the mean score p value of 0,05 will be deemed significant.

A power analysis will be conducted for a subsequent study, based on the results of this pilot trial.

As there is no data for VR teaching in terms of medical procedures in anaesthesia this study will provide a baseline comparison to traditional teaching. Certainly, an increase of 20% in the mean score would be seen as significant.

Statistical plan deviations

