There is no anticipated deviation from the scoring system used to assess the placement of the chest drain. Incomplete scoring systems will not be included in the final analysis but may be used to make trends in comparisons between the two groups. Should any unanticipated protocol deviation occur this will be reported to the hospital ethics committee and a decision to proceed further will be made by the investigators.

Selection of participants for analyses

Participant selection will be via a convenience sampling of Anaesthesia Registrars from the Department of Anaesthesia and Pain Medicine at FSFHG. All consenting and participating registrars will be included in the final analysis of the two teaching methods employed in the study.

Data Management

All of the participate data will be anonymised and deidentified. The data will be stored on the chief investigator's password protected work computer. The data will only be accessible by the research team. The computer is locked in a cupboard in the anaesthetic department, which is only accessible by staff access security badges. Access to this data will be further blocked by passwords to specific folders minimizing access. No personal data will be shared with any 3rd party sponsors or external teams. Data including electronic, hardcopy and consents will be stored for a period of 7 years from the period of publication and will be made available should a written request be made by the ethics committee or hospital board. The data, hardcopies and consents will be destroyed after 7 years.

Procedure for accounting for missing, unused, and spurious (false) data.

All collected data will be analysed by each member of the investigating team. Incomplete data will not be included in the final analysis. Incomplete data may be used to analyse trends in the data from which no final conclusions will be drawn. Incorrectly completed checklists will not be utilised for final analysis.

9 Monitoring / Audit

Monitoring, Audit and Regulatory Inspections Statement

The project investigators/institutions will permit project-related monitoring, audits, and regulatory inspections, providing direct access to source data/documents. This may include, but not limited to, review by external sponsors, Human Research Ethics Committees and institutional governance review bodies.

Procedures for Monitoring and auditing

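### Protocol section 8 promises to analyse every participating registrar but also excludes incomplete data and incorrectly completed checklists, with neither term defined and no blinded decision on what is unusable

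*Protocol*

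**What the plan says.** Four statements in Protocol section 8 bear on who is analysed.

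- Statistical plan deviations: "Incomplete scoring systems will not be included in the final analysis but may be used to make trends in comparisons between the two groups".
- Selection of participants for analyses: "All consenting and participating registrars will be included in the final analysis of the two teaching methods employed in the study".
- Procedure for accounting for missing, unused, and spurious (false) data: "Incomplete data will not be included in the final analysis". Such data may be looked at for trends, but no final conclusion may rest on them.
- The same subsection: "Incorrectly completed checklists will not be utilised for final analysis".

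Three other places matter. Section 8, Study Power and Significance, describes the instrument: "This checklist has 20 steps, graded out of 40 points, that must be completed in order for the chest drain placement to be deemed safe". Section 6 lists the outcomes, which include "Raw scores on the validated chest drain insertion competency checklist", "Any deviation from the validated checklist" and the time taken. Section 4, Project Design, says "All study participants will be assessed by two anaesthetic consultants blinded to group allocation". Under Blinding and Randomisation, section 4 adds that the researchers keep the allocation list and match it to the assessors' score sheets.

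**The concern.** The protocol fixes two rules for the analysis population that differ whenever a record is defective. Two analysts could report different populations, and each could claim to have followed the plan.

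The exclusion terms are also open. *Incomplete* may mean a form that the assessor did not fill in, or an attempt in which the registrar left steps undone. Section 8 itself speaks of the steps being completed when it describes the procedure. Under the second meaning, exclusion is related to the outcome. Completion time has the same difficulty in a plainer form: someone who never finishes has no time, and so has incomplete data for that outcome.

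If such exclusions fall more heavily on one arm, the comparison of the two teaching methods is biased. The pool is at most 51 registrars, so each loss counts. The results are also meant to feed the power calculation for a follow-up study, and a bias here would carry into it.

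**Working it through.** **The contradiction.** The Selection subsection admits every consenting and participating registrar. The other two subsections exclude incomplete scoring, incomplete data and incorrectly completed checklists. Take a registrar who consents, trains and is assessed, but whose sheet has a blank item. The first rule keeps the record and the second removes it. No sentence ranks one above the other. This needs no assumption.

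**What is undefined.** The protocol does not say:

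- what makes a sheet incomplete or incorrectly completed;
- how an abandoned attempt is recorded;
- what happens when one assessor's sheet is sound and the other's is not;
- who decides that a sheet is unusable, and whether that person is blind to allocation.

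**Possible size.** The protocol gives no mean, SD or expected number of exclusions, so there is no figure to reproduce. What follows is illustrative.

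*Shift in one arm's mean.* If the lowest fraction q of a normal distribution is removed, the mean rises by φ(z_q)/(1 − q) SD. Assume an arm of 25, about half of 51.

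| Dropped | q | φ(z_q) | φ(z_q)/(1 − q) |
|---|---|---|---|
| 2 of 25 | 0.08 | 0.149 | 0.149/0.92 = 0.16 SD |
| 3 of 25 | 0.12 | 0.200 | 0.200/0.88 = 0.23 SD |
| 5 of 25 | 0.20 | 0.280 | 0.280/0.80 = 0.35 SD |

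Calculated for the exact counts in an arm of 25, the shifts are slightly smaller: 0.153, 0.217 and 0.337 SD.

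*Simulation.* Assumptions: control mean 28 of 40, SD 5 or 7, scores cut to 0–40, arms of 25 and 26, two-sided Mann-Whitney test at 0.05. Means rest on 40,000 simulated trials and rejection rates on 4,000.

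| Scenario | Mean difference, SD 5 | Mean difference, SD 7 | Rejection rate |
|---|---|---|---|
| No true difference, nobody dropped | 0.0 | 0.0 | 5% |
| No true difference, lowest 3 dropped from one arm | 1.0 to 1.1 points either way | 1.4 to 1.5 either way | 10–12% |
| No true difference, lowest 5 dropped from one arm | 1.6 to 1.7 either way | 2.3 either way | 20–21% |
| No true difference, lowest 3 dropped from each arm | about 0 | about 0 | 7–8% |

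The protocol calls a 20% gain in mean score significant. On the assumed control mean this is 28 × 1.2 = 33.6. With everyone analysed, the mean difference is 5.4 points (SD 5) or 5.0 (SD 7), less than 5.6 because of the ceiling at 40. Deleting every score below one fixed cut in both arms gives:

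| Cut | SD 5 | SD 7 |
|---|---|---|
| 20 | 5.4 falls to 4.8 | 5.0 falls to 3.8 |
| 24 | 5.4 falls to 3.9 | 5.0 falls to 2.9 |

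A common performance cut therefore shrinks a true difference, because the weaker arm loses more people. Deletion from one arm alone moves the result in a direction that depends on which arm loses people.

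**The case against.** The strongest reply is that these are rules about paperwork. Two consultants complete the checklist, not the registrar, so an incomplete or incorrectly completed sheet most naturally means an assessor's error. The design also expects imperfect attempts to be scored: deviations are counted as an outcome, and 20 steps are graded out of 40 points. That would make little sense if an omitted step voided the sheet. The checklist itself, listed as an appendix, is not shown and may say how an unperformed step is graded. The selection sentence can also be read as defining the population and the others as complete-case handling, so that they collide only when a sheet is defective. Excluded data may serve only for trends without final conclusions, and the study is a pilot.

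Much of this stands. A reader might infer that the rule does remove failed attempts. The text does not say so, and no section says that an undone step is left blank. A reader might also infer that one blank item removes the whole participant despite a second assessor's sheet. The wording excludes scoring systems, data and checklists, and is silent on that.

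It does not dispose of the point. Nothing limits the exclusions to assessor error, and the paperwork reading gives no help with a participant who has no completion time. Nor is this a detail left to a statistical analysis plan, because the protocol states the exclusion and contradicts it.

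**Conclusion.** The point holds as a contradiction in the stated analysis population, made worse by undefined exclusion terms and the absence of a blinded decision on unusable sheets. Wrongly applied, the rules could make exclusion depend on performance, with bias if the arms differ in how many they lose.

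The size is unknown. The 0.16 to 0.35 SD range assumes that exactly the lowest scorers are dropped, from one arm only, at rates the protocol does not give. It shows what the wording would allow and is not a forecast.

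Two stronger conclusions are not supported. A reader might infer that investigators who know the allocation decide which sheets to discard. The researchers hold the list, but no section says who makes that decision; the gap itself is the finding. A reader might also infer that the rule could reverse a true effect. In the illustration with a 20% gain, a common cut reduces the difference but leaves it positive, and the protocol offers no exclusion rate from which a reversal could be argued.

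This should be corrected before the data are analysed.

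**What to change.** Replace the exclusion rules in both subsections of section 8 with one text that agrees with the Selection subsection:

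> All randomised participants who are assessed are analysed in their allocated group. A step not performed is scored as not performed and counted as a deviation; it is not missing data. If one assessor's sheet is incomplete or unusable, the other assessor's sheet is used. Whether a sheet is unusable is decided before allocation is linked, and exclusions are reported by arm. A participant who does not finish is kept in the time analysis under a pre-stated convention (for example, ranked worst).

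This assumes that each of the two assessors fills in a separate sheet, which section 4 suggests but does not spell out; a short clause should confirm it. The text covers assessed participants only and leaves the section 4 exclusion and withdrawal criteria untouched.

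The cost is protocol wording. The one small downside is that a convention for non-finishers' times has to be chosen. Ranking them worst is one option among several, and whichever is chosen should be fixed before allocation is linked.
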